6.4.4 Other safety variables

Other safety variables include vital signs (systolic and diastolic blood pressure, pulse rate).

6.4.5 Analysis of safety variables

The analysis of the primary and secondary safety variables will be based on the SAF and on-treatment data scope.

Time to the first occurrence of the primary safety endpoint (i.e., TIMI major bleeding) will be compared using a Cox proportional hazards model stratified by type of procedure and use of clopidogrel (per IxRS assignment) with treatment group as a covariate. A plot of cumulative event rate derived by Kaplan-Meier estimate will be provided to show event rate and treatment effect by time.

The secondary safety outcome variables will be analyzed similarly.

As supportive analyses, the primary safety variable will be analyzed as described above based on the SAF and ITT data scope as well as overall study duration including post-study treatment follow-up. In addition, the primary safety variable will be analyzed according to the actual qualifying revascularization procedure (section 6.2.9) and in subgroups as described in section 6.2.4. Number of subjects with multiple TIMI major bleedings will also be summarized in frequency table.

As exploratory analyses, landmark analysis similar to those as described in section 6.2.8 will also be performed for the primary safety variable.

Additionally number of patients with bleeding leading to permanent drug discontinuation will be summarized by bleeding sites.

Concordance of ICAC and investigator reports on the TIMI major bleeding events will be provided for the combined treatment group.

Other safety variables will be summarized descriptively.

Any pregnancy occurring in a study subject during the subject's participation in this study will be displayed.

Statistical Analysis Plan

Protocol No.: **BAY 59-7939 / 17454**

Page: 28 of 36

6.5 Other procedures and variables

The other procedures and variables include:

- Health care resource utilization data
- PAD symptom status

For these variables, additional analyses other than those specified in sections [6.2.7](#) and [6.2.8](#) may be performed and reported separately.

6.6 Benefit/Risk Assessment

The benefit-risk analyses are structured to allow an integrated evaluation of the key benefits and risks in the study. They are complementary to the efficacy and safety analyses described previously in this document and not intended for hypothesis testing. These analyses will be performed in patient populations with the same follow up. Details of these analyses will be described in a separate document (supplemental statistical analysis plan for benefit-risk).

The benefit-risk evaluation will be based on the comparison of the time-to-first-event rates (rivaroxaban added to ASA vs. ASA alone), for events intended to be prevented (benefits) and events that may be caused (risks). Individual outcome measures balanced and weighed by clinical significance and severity will be compared to evaluate the trade-off between prevention of thrombotic vascular events versus harm (i.e. bleeding). These outcome measures include the individual components of the primary efficacy outcome, risk measurements include the hemorrhagic events of the efficacy endpoint and bleedings according to TIMI classification. To have a comprehensive benefit-risk evaluation, several quantification methods will be used.

Results of the above analysis do not preclude additional benefit/risk assessment in other endpoints. The overall benefit-risk profile of the study drug will be interpreted in consideration of the totality of the data.

7. Document history and changes in the planned statistical analysis

Version	Date	Action
Draft SAP submitted to FDA	12 June 2015	
Version 1.0	7 April 2016	Updates based on protocol amendment #4 and FDA feedback on planned sensitivity analyses to assess the impact of missing data
Version 2.0	14 May 2018	
• Order of secondary efficacy endpoints were changed according to Global Integrated Clinical Study Protocol version 3.0• Efficacy cut-off date and censoring rules for efficacy endpoints were modified in

Statistical Analysis Plan

Version	Date	Action
		
section 4.5.1, 4.5.3 and Appendix A
 
 Added a few more subgroup variables in section 6.2.4 Added more exploratory analyses (e.g. MACE/MALE endpoints, landmark analysis for primary efficacy endpoint) in section 6.2.8 Added more sensitivity analyses of primary and secondary efficacy endpoints in section 6.2.10 Added AEs analyses for Japan vs. non-Japan patients in section 6.4.1, and supportive analyses in section 6.4.5. Updated benefit/risk analysis in section 6.6 Added Appendix B for the definition of regions Added Appendix C to describe the mathematical details of the tipping point analysis
Version 3.0	24 July 2019	
None of the edits in this SAP version is considered to change the primary efficacy analysis and other analyses as described in the SAP version 2.0, but includes further clarifications and additional analyses.
 
Editorial, administrative, and typographical corrections were made that do not affect the overall SAP. These changes are not described in this section.
 
The following changes are introduced in SAP version 3.0:
 
 Added information on imputation rules for the missing or incomplete post-randomization event dates in section 4.3 Added information on derivation of the first dose and last dose date of study treatment in section 4.5.1. Added analysis in data scopes with overall study duration for sensitivity analysis in section 4.5.2 Added information on censoring rules for efficacy endpoints in section 4.5.3 and

Statistical Analysis Plan

Version	Date	Action
		
Appendix A
 
Added analysis on SAF with on-treatment data scope for secondary efficacy endpoints, subgroup variables, and changed sensitivity analysis for primary efficacy endpoints with on-treatment data scope from ITT to SAF in Table 1Updated some demographic variables in section 6.1.2Updated other efficacy variables in section 6.2.3Updated some subgroup variables in section 6.2.4Updated SAS code to display both one-sided and two-sided p values in section 6.2.5Updated exploratory analysis with detailed statistical model information in the multiple occurrences of the primary efficacy endpoints analysis and references in section 6.2.8Updated exploratory analysis in the subgroup variables in section 6.2.8Added additional landmark analysis on the time period from randomization to 6-month, 6-month to 1 year and 1-year to end of treatment phase in section 6.2.8Added likelihood ratio test analysis to test for interaction terms in the subgroup analysis in section 6.2.9Added sensitivity analyses on individual components of primary efficacy endpoints on SAF and on-treatment data scope in section 6.2.10Updated sensitivity analyses on the missing data tipping point analysis by including the additional baseline covariates in the Cox model in section 6.2.10Removed European quality of life 5 dimensions questionnaire and walking impairment questionnaire variables in section 6.5. Those variables were

Statistical Analysis Plan

Version	Date	Action
		
mentioned in section 6.2.3
 
• Updated Efficacy cut-off date, timelines, and censoring variables in Appendix A• Added Appendix D for the detailed information on imputation rules for missing dose date• Added Appendix E for the definition on the components of the primary efficacy outcome by the investigators

8. References

Andersen, PK and Gill, RD: Cox's Regression Model for Counting Processes: A Large Sample Study. *Annals of Statistics*, 1982; 10:1100-1120.

Austin PC. A Tutorial on Multilevel Survival Analysis: Methods, Models and Applications. *Int Stat Rev*. 2017;85(2):185–203. doi:10.1111/insr.12214.

Appendix A: Study Closeout Procedure and Variables used for Censoring

Note: The dates and timeline shown are for illustration purpose only. ECOD= Efficacy cut-off date, EOT Visit=end of treatment visit, PS-FU Visit=Post-study treatment follow-up visit (phone call), DBL=database lock

The executive committee will monitor the accrual of the number of primary events, and when appropriate predict and define an ECOD at which time the pre-defined target number of events for the primary composite endpoint are expected to have occurred. All randomized patients should return for their End of Treatment (EOT) visit after the ECOD.

Events that occur after the ECOD will also be collected and adjudicated. These events will be included in sensitivity analyses but not the primary analysis.

For the implementation of the censoring rules below variables are defined to distinguish between a patient's last contact with information relating to clinical events versus CV-death / all-cause mortality.

- Date of objection to further data collection

This date will be given only for those subjects who expressed objection to further data collection after withdrawal of informed consent.

- Last clinical event ascertainment date

The latest date from regular or unscheduled post-randomization visits or contacts with assessment of clinical events or latest adjudicated clinical event start date.

- Date of last contact alive

The date of the last documented contact with the subject or a third party (including data on subject survival status) derived from the maximum (last clinical event ascertainment date, SAEs date, vital status date, consent withdrawn date or date of objection to further data collection). The resulting maximum date is capped by the death date if the patient died or by the date of clean database. In addition, the date of last contact alive will be the day before the death date, if available, for subjects who die.

Statistical Analysis Plan

Protocol No.: **BAY 59-7939 / 17454**

Page: 33 of 36

Appendix B: Definition of Regions

Countries will be assigned to regions as shown in Table 2 below. If additional countries participate in the trial, their assignment to a region will be specified in the table/listing/figure specification document before unblinding.

Table 2 Classification of Countries to Regions

Region	Countries
North America	Canada, USA
Western Europe	Austria, Belgium, Denmark, Finland, France, Germany, Italy, Netherlands, Portugal, Spain, Sweden, Switzerland, United Kingdom
Eastern Europe	Bulgaria, Czech Republic, Estonia, Hungary, Latvia, Lithuania, Poland, Romania, Russia, Serbia, Slovakia, Ukraine
Asia Pacific	China, Japan, South Korea, Taiwan, Thailand
South America	Argentina, Brazil

Appendix C: Mathematical Details of the Proposed Tipping Point Analysis

The robustness of the treatment effect with respect to missing data will be evaluated with a tipping point analysis for the primary efficacy variable. A methodology similar to pattern-mixture-models will be employed, where a Weibull survival model will be fitted to impute outcome for subjects who are lost-to-follow-up (or withdrawn consent with no further information) ([Little 2016](#)).

1. Estimate the hazard at time of loss to follow-up, adjusting for treatment group, covariates and stratification factors
 - a. The log survival time $w = \log(t)$ is modeled using SAS LIFEREG procedure by fitting a Weibull distribution to all subjects, adjusting for treatment group, covariates and stratification factors. The survival function has the form
$$S_0(w) = \exp\left(-\exp\left(\frac{w-\mu}{\sigma}\right)\right),$$
where μ (differs for treatment, covariates, and stratum) and σ (scale) are estimated from the SAS output.

- b. Re-parametrize the Weibull distribution with survival function

$$S(t) = \exp(-(t/\lambda)^\beta),$$

where λ is the scale parameter and β is the shape parameter. Obtain the estimates of λ and β as

$$\lambda = \exp(\mu)$$

$$\beta = 1/\sigma.$$

- c. Obtain the observed hazard rate for individual subjects using the hazard function

$$h(t|\lambda, \beta) = (\beta/\lambda) (t/\lambda)^{\beta-1}.$$

Statistical Analysis Plan

2. Inflate the hazard only in the rivaroxaban group by a set of inflation factors; assuming non-informative censoring in the control group

Let k be the inflation factor, the inflated hazard rate in the rivaroxaban group is

$$h^*(t|\lambda, \beta) = k \times (\beta/\lambda) (t/\lambda)^{\beta-1}$$

and the new scale parameter is

$$\lambda^* = \lambda / (k^{1/\beta})$$

by solving λ^* from $k \times (\beta/\lambda) (t/\lambda)^{\beta-1} = (\beta/\lambda^*) (t/\lambda^*)^{\beta-1}$, while fixing the shape parameter β .

The hazard rate in the control group remains unchanged.

3. Perform simulations to impute events to the end of the study using standard multiple imputation rules ([Rubin 1987](#)), and compute the hazard ratio and two-sided 95% CI using the primary Cox proportional model

For subjects who are lost-to-follow up (or withdrawn consent with no further information), and who did not experience a primary efficacy endpoint prior to the ECOD, random variables will be simulated using the conditional time to event distribution after the last contact date (LC) (defined as earlier date of last clinical event ascertainment date, date of the objection to further data collection) given that no event was observed before.

Let x be the time from the last contact date (LC) to the event date, the conditional probability of having an event given no event observed before LC is

$$\begin{aligned} y &= \Pr(t \leq x + LC \mid t > LC) = 1 - \Pr(t > x + LC \mid t > LC) \\ &= 1 - \frac{\Pr(t > x + LC)}{\Pr(t > LC)} = 1 - \frac{S(x + LC)}{S(LC)}. \end{aligned}$$

Using the estimated scale parameter λ^* and shape parameter β from Weibull distribution in step 2, the above becomes

$$\begin{aligned} y &= 1 - \exp(-(x + LC)/\lambda^*)^\beta / \exp(-(LC/\lambda^*)^\beta), \\ &\Leftrightarrow \log(1-y) = -((x + LC)/\lambda^*)^\beta + (LC/\lambda^*)^\beta \\ &\Leftrightarrow x = \lambda^* ((LC/\lambda^*)^\beta - \log(1-y))^{1/\beta} - LC. \end{aligned}$$

If y is generated as a random variable with uniform distribution between 0 and 1, the random variable x can be generated using the inverse transformation technique from the formula above.

If this randomly generated variable has a value less than the elapsed time between the last contact date and the efficacy cut off date, the subject will be counted as having observed an event at the last contact date plus the random variable. Otherwise, the subject is re-adjusted to be censored at the ECOD.

Statistical Analysis Plan

Protocol No.: **BAY 59-7939 / 17454**

Page: 35 of 36

These imputed events will be added to the observed events in the study for both treatments and the primary efficacy variable will be re-analyzed. This process will be repeated 1000 times. The hazard ratio with 95% CI will be estimated for each imputed data set and then combined using standard multiple imputation combining rules.

- Given the study results is statistically significant in favor of rivaroxaban, increase the inflation factor (by repeating steps 2 and 3) until the upper limit of the two-sided 95% CI for the hazard ratio crosses 1.0; this will be the “tipping point”.

Reference:

Appendix D: Imputation Rules for Missing Dose Date

First dose date is missing or incomplete	Action
Only day of first dose date is missing	Impute the first dose date as maximum (date of randomization+1 day, 01.month.year)
Month and day of first dose date is missing	Impute the first dose date as randomization + 1 day.
First dose date is complete missing but last dose date is available	Impute the first dose date as randomization + 1 day.
First dose date and last dose date is missing	The patient never took the study medicine
Last dose date is missing or incomplete	Action
Only day of last dose date is missing	
Impute the last dose date using last day of the monthDerive last dose date as minimum of (the date of last contact, imputed last dose date, the date of death, or the maximum of (ECOD, EOT visit date)) but no earlier than the date of first dose.
Month and day of last dose date is missing	
Impute the last dose date using last day of the yearDerive last dose date as minimum of (the date of last contact, imputed last dose date, the date of death, or the maximum of (ECOD, EOT visit date)) but no earlier than the date of first dose.
Last dose date is complete missing but first dose date is available	Impute last dose date as minimum of (the date of last contact, the date of death, or the maximum of (ECOD, EOT visit date)) but no earlier than the date of first dose.

Statistical Analysis Plan

Protocol No.: **BAY 59-7939 / 17454**

Page: 36 of 36

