#### **7.4.1 Dose modifications**

The investigator should interrupt study medication and/or study ASA for a given patient if continuation is deemed to be detrimental to the patient's well-being. All patients who interrupt study medication and/or study ASA should resume treatment when possible. If there is concern that the patient may be intolerant of study treatments or if the patient is reluctant to take the full dose of study medication, a possible approach to restarting study medications is to reduce the frequency of dosing to once-daily or alternate-daily.

Irrespective of whether or not treatment is resumed, all patients must be followed according to the study protocol until the end of the study. Permanent study drug discontinuation should be recorded on the eCRF, giving the date and primary reason for stopping the study medication and/or study ASA. If one of the study treatments needs to be interrupted, other study treatments should be continued. For example, if study medication is interrupted, study ASA should be continued.

This section provides a general guide for investigators on the management of patients who develop intercurrent illnesses or bleeding during the course of the study. The guidance provided in this section does not replace clinical judgment nor usual care in determining the appropriate management strategy for individual patients.

The following sections provide general guidance for use of rivaroxaban. For use of ASA, please refer to applicable guidelines and local production information.

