4.5 Data Rules

4.5.1 Analysis Dates

For the study, the following date and time window are of relevance for the analysis:

- Efficacy cut-off date:
The trial is designed to be terminated when 1015 patients have experienced a confirmed primary efficacy outcome event. The ECOD is a predicted common date when at least 1015 primary efficacy outcomes are expected to have occurred. It is the last calendar date acceptable for counting events for the primary analysis.
- Trial close-out window:
The time period when all subjects return to the clinic for an EOT visit. All randomized subjects should return for their EOT visit after the ECOD.

For each subject, the following individual dates are of relevance for analysis:

- Randomization date:
The date of randomization as recorded in the IxRS system.
- EOT Visit date:
The date of the EOT visit. If subjects do not have an EOT visit, the date will be missing.
- Date of last contact:
The date of the last documented contact with the subject or a third party (including data on subject survival status, see [Appendix A](#) for details).
- Date of first dose of study treatment:
The date of the first dose of rivaroxaban or rivaroxaban placebo, defined as:
 - Date of first dose from the appropriate CRF page capturing the study medication (rivaroxaban or rivaroxaban placebo) if this date is complete.
 - Date of the earliest logically possible dose of study medication (rivaroxaban or rivaroxaban placebo) administration in cases where the date of first dose is missing or incomplete. See [Appendix D](#) for details of the imputation rules.
- Date of last dose of study treatment:

Statistical Analysis Plan

Protocol No.: **BAY 59-7939 / 17454**

Page: 11 of 36

The date of the last dose of rivaroxaban or rivaroxaban placebo, defined as:

- Date of last dose from the appropriate CRF page capturing the study medication (rivaroxaban or rivaroxaban placebo) if this date is complete.
- Date of the latest logically possible dose of study medication (rivaroxaban or rivaroxaban placebo) administration in cases where the date of last dose is missing or incomplete. See [Appendix D](#) for details of the imputation rules.

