4.5.2 Data Scopes

All analyses are based on two elements:

- 1) *analysis set*, which specifies which subjects will be included in an analysis; and
- 2) *data scope*, which specifies the time window within which data will be included in an analysis.

This section describes the coverage of the event *data scopes* used for the statistical analyses. *Analysis sets* are described in Section 5.

Data scope according to intention-to-treat principle (ITT)

The ITT data scope includes outcome events observed from randomization date until the ECOD. Events occurring after the ECOD will not be counted for primary analysis. This ITT data scope will be applied mainly to the analyses of efficacy variables.

Data scope according to treatment (on-treatment)

The on-treatment data scope will include all outcome events observed from randomization until 2 days following permanent discontinuation of the study drug. This on-treatment data scope will be applied mainly to the analyses of safety variables (e.g. bleeding).

Data scope according to overall study duration for sensitivity analysis

The overall study duration data scope will include all outcome events observed from randomization until the last contact/visit. This data scope will be applied for sensitivity analysis only.

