4.5.3 Censoring rules for time-to-event variables

All efforts will be made to collect complete data for all subjects randomized in this study including visits by telephone contact.

Censoring rules for analyses according to the ITT principle

The censoring rule for time to first event analyses depends on the type of endpoint, thereby distinguishing between clinical events endpoints (primary efficacy composite and component, secondary efficacy and bleeding events) and CV-death / all-cause mortality.

Statistical Analysis Plan

Protocol No.: **BAY 59-7939 / 17454**

Page: 12 of 36

	Primary efficacy composite and components other than CV-death	All-cause mortality, CV-death
If the subject was randomized but has no post-randomization clinical event ascertainment date the subject will be censored :	At the randomization date + 1 day	Earlier of last contact alive date or ECOD If no last contact alive date, use the randomization date +1 day
Else, if the subject has withdrawn from the study but objected to further data collection the subject will be censored :	At the earlier date of the last clinical event ascertainment date (LCEAD), date of objection to further data collection or ECOD	Earlier of last contact alive date from public sources or ECOD If no last contact alive date from public sources, use the earlier date objection to further data collection or ECOD
Otherwise, the subject will be censored :	At the earlier date of last clinical event ascertainment date, date when patient died or ECOD	At the earlier date of last contact alive date or ECOD

Censoring rules for analyses according to the on-treatment principle

For on-treatment analyses (primary analysis for time to bleeding events, sensitivity analysis for primary efficacy endpoint and all secondary efficacy endpoints), patient with at least one dose of study medication and without documentation of an event within the on-treatment data scope will be censored similarly to the ITT data scope except that the date of last dose of study treatment + 2 days will be used as the cap for the time scope instead of ECOD.

Censoring rules for analyses according to the overall study duration principle

Above censoring rules for ITT data scope apply except that the date of last clinical event ascertainment or last contact alive will be used as the cap for the time scope instead of ECOD.

See [Appendix A](#) for additional details.

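### SAP Appendix D does not bound a wholly missing last-dose date at a recorded permanent discontinuation, so some off-drug time can count as on-treatment in the bleeding analyses; the effect is probably very small

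*SAP*

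**What the plan says.** SAP 4.5.1 uses the CRF last-dose date when it is complete. Otherwise it calls for the "Date of the latest logically possible dose of study medication (rivaroxaban or rivaroxaban placebo) administration" and leaves the details to Appendix D, which has three rows for the last dose:

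- **Completely missing, first-dose date available:** "Impute last dose date as minimum of (the date of last contact, the date of death, or the maximum of (ECOD, EOT visit date", not before the first dose.
- **Year only:** last day of that year, under the same limits.
- **Month and year:** last day of that month, under the same limits.

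SAP 4.5.1 defines last contact broadly: "The date of the last documented contact with the subject or a third party".

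Two sections then set the on-treatment window. SAP 4.5.2 states: "The on-treatment data scope will include all outcome events observed from randomization until 2 days following permanent discontinuation of the study drug". SAP 4.5.3 states, for censoring, that "the date of last dose of study treatment + 2 days will be used as the cap for the time scope instead of ECOD". The window matters because of SAP 6.4.5: "The analysis of the primary and secondary safety variables will be based on the SAF and on-treatment data scope".

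On data collection, Protocol 7.4.1 requires: "Permanent study drug discontinuation should be recorded on the eCRF, giving the date and primary reason". Protocol 7.7 separately collects the last-dose date. Under Protocol 6.3.1 and SAP section 3, patients who stop drug remain in follow-up to study end, by telephone if necessary.

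**The concern.** A patient can be recorded as permanently off drug, have no last-dose date, and still be in follow-up years later. Appendix D then places the last dose at last contact or around the efficacy cut-off date (ECOD), because none of its limits refers to the stop. Through the cap in SAP 4.5.3, the whole off-drug period becomes time at risk on treatment.

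This date governs the primary safety outcome (TIMI major bleeding), the ISTH and BARC outcomes, treatment duration (SAP 6.1.6) and the on-treatment sensitivity analyses of efficacy. Off-drug time blurs the contrast that the on-treatment analysis is meant to isolate. Added to both arms, it pulls a bleeding hazard ratio toward 1 and overstates exposure.

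The rule also sits badly with the rest of the SAP. A dose after a recorded permanent stop is not a logically possible dose in the sense of 4.5.1. For such a patient, 4.5.2 and 4.5.3 can end the window years apart.

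**Working it through.** **1. Error per patient.**

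- *Date completely missing (assumed timing):* the patient stops at month 6 and is followed to month 42. The imputed last dose is about month 42, so 42 − 6 = 36 off-drug months count as on-treatment.
- *Year only:* a stop early in January becomes 31 December, so at most about 12 months.
- *Month known:* a stop on day 1 of a 31-day month becomes day 31, so at most 30 days.

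**2. Reproduce the plan's own figure.** The discontinuation model that sizes the problem is the one behind the 1,015 events in SAP 4.6. Inputs, all from SAP 4.6:

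- HR 0.80, one-sided alpha 0.025, 90% power, 6,500 patients randomized 1:1;
- control rate 7.5% per year;
- permanent discontinuation 5.5% in year 1, 8% in year 2, 4% + 8% in the halves of year 3, then 8% per half year;
- loss to follow-up or non-CV death 1.5% per year;
- accrual 15/30/55% over 18 months, then 24 months of follow-up.

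Without discontinuation, the Schoenfeld formula gives 4 × (1.960 + 1.282)² / (ln 0.80)² ≈ 845 events. A Lakatos-type log-rank calculation, with stopped rivaroxaban patients reverting to the control hazard and 7.5% used as a hazard, gives 1,014 events from 6,500 patients, 89.9% power, and 1,018 events needed for 90%. That agrees with the plan's 1,015.

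**3. Off-drug time in the rivaroxaban arm, same model.** About 527 patients stop permanently before cut-off (527 / 3,250 = 16.2%). On-drug time is 6,928 patient-years and off-drug time 593, together 7,521. The off-drug share is 593 / 7,521 = 7.9%, or 593 / 527 ≈ 1.1 years per discontinuer.

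**4. Effect on the bleeding hazard ratio.** The documents give neither the share *m* of discontinuers with a completely missing date nor any bleeding rate, so both are ranges. Assume *m* is the same in both arms and the off-drug bleeding rate equals the control rate. Using rate ratios as an approximation to the Cox estimate:

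estimated HR = (HR × 6,928 + *m* × 593) / (6,928 + *m* × 593)

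| *m* | Patients | Off-drug patient-years | Share of counted time | True HR 1.25 | True HR 1.5 | True HR 2.0 |
|---|---|---|---|---|---|---|
| 1% | 5 | 5.9 | 0.09% | 1.250 | 1.500 | 1.999 |
| 10% | 53 | 59 | 0.9% | 1.248 | 1.496 | 1.992 |
| 25% | 132 | 148 | 2.1% | 1.245 | 1.490 | 1.979 |
| 100% | 527 | 593 | 7.9% | 1.230 | 1.461 | 1.921 |

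If the off-drug rate is half the control rate in both arms, the shift is smaller: at *m* = 25%, a true HR of 1.5 is estimated as 1.495.

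**5. Time versus events.** Off-drug time enters directly through the cap in SAP 4.5.3. Off-drug events enter only if the event window is also programmed from the imputed last dose. If it follows SAP 4.5.2 and the recorded stop, they do not. The SAP does not say which governs.

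**The case against.** The strongest reply is that the gap will seldom be reached. A complete CRF date always takes precedence, and the protocol requires both a discontinuation date and a last-dose date. TIMI major bleeding is also analysed in the safety set under the ITT scope and over the overall study duration (SAP Table 1 and 6.4.5), both of which deliberately include off-drug time. Under Protocol 10.5 no formal safety boundary depends on the result. All of this stands, and it is why the point is minor. It does not supply the missing bound: the supportive analyses answer a different question, and the on-treatment analysis is the main one.

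Four stronger readings are tempting but unsupported:

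- *Every patient who stops and is then followed by telephone is analysed as on treatment to study end.* This requires a last-dose date with no day, month or year.
- *Off-drug bleeds certainly enter the primary safety analysis.* SAP 4.5.2 ends the event window 2 days after permanent discontinuation, so this depends on programming.
- *A survival-only check with a third party prolongs bleeding time at risk.* It can prolong the exposure summaries. In the time-to-event analyses, however, SAP 4.5.3 still censors at the last clinical event ascertainment if that is earlier.
- *The row for two missing dose dates ("The patient never took the study medicine") drops treated patients from the safety set.* The first dose is given on site at the randomization visit (Protocol 9.2.1.2), both dates are collected, and SAP 4.2 recognises patients who never started. Nothing in the documents shows that treated patients would lack both dates.

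**Conclusion.** The point holds as a narrow gap. As written, Appendix D lets off-drug time count as on-treatment when the last-dose date is wholly missing, and to a limited extent when it is partial. This conflicts with SAP 4.5.2 and with the principle in 4.5.1.

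Under the assumptions above, the bias in the bleeding hazard ratio is toward 1. It is about 0.02 at most if a quarter of discontinuers lacked a date (0.005 to 0.021 for true hazard ratios of 1.25 to 2.0), and about 0.08 at most if all did. The direction rests on equal shares of missing dates and equal off-drug bleeding rates in the two arms. The true share is unknown and, since the date is a required eCRF item, probably low. A reader might infer that the bleeding conclusion is at risk; these figures do not support that. This is a clarification worth making, not a threat to the trial.

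**What to change.** In each of the three minimum lists for the last-dose date in Appendix D, add one term: the recorded date of permanent discontinuation or, if that is missing, the date of the first visit or contact at which permanent discontinuation was recorded. If that date falls before a recorded month or year of last dose, treat the conflict as a data query. Report the number of imputed last-dose dates per arm, split by completely missing, year only, and month and year.

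A nominal run-out date for the last dispensed supply should not be added as a cap. Interruptions have no maximum length (Protocol 6.3.1) and reduced-frequency dosing is permitted (7.4.1). Tablets can therefore outlast the nominal date, and the cap could remove real on-drug time or contradict a recorded month.

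The cost is one phrase in three rows and one line in a table, made before unblinding and using data already collected. For patients with a recorded stop it also brings the windows in SAP 4.5.2 and 4.5.3 back into line.
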